Appendix 3. Protocol Version 3.0 has been added to record changes made to this protocol.

# 2 Modification History

Unique Identifier for this Version	Date of the Document Version	Author	Significant Changes from Previous Authorized Version
0.1	11MAR2020	[name]	n.a.
0.2	30APR2020	[name]	Previous released used for internal revision and comments from Catalyst Pharmaceuticals.  Minor changes done to the methodology text.  Added summary tables of each individual item of HFMSE  Provided shells of all line listings
1.0	11MAY2020	[name]	Approved version.

# 3 List of Abbreviations and Definitions of Terms

Abbreviation	Definition
6MWT	Six-minute walk test
3,4-DAP	3,4-diaminopyridine
AChR-MG	Acetylcholine receptor Myasthenia Gravis
ADL	Activities of Daily Living
ADME	absorption, distribution, metabolism, and excretion
AE(s)	adverse event(s)
ALS	amyotrophic lateral sclerosis
ALT	alanine aminotransferase
ANS	autonomic nervous system
AST	aspartate aminotransferase
ATU	Autorisations Temporaires d'Utilisation Normative
AUC	area under the plasma concentration-time curve
$AUC_{0-\infty}$	area under the plasma concentration-time curve from time 0 to infinity
BMI	Body mass index
CI	confidence interval
$C_{\text{max}}$	peak plasma concentration
CFB	Change from baseline
CMS	congenital myasthenia syndromes
CNS	central nervous system
CRA(s)	clinical research associate(s)
CRF	case report form
CRO	contract research organization
CYP450	cytochrome P450
DBP	diastolic blood pressure
ECG(s)	electrocardiogram(s)
eCRF	electronic case report form
EFNS	European Federation of Neurological Societies
FAS	Full Analysis Set
FDA	Food and Drug Administration
GCP	Good Clinical Practice
hERG	human Ether-à-go-go Related Gene
HFMSE	Hammersmith Functional Motor Scale Expanded
ICF	informed consent form
ICH	International Conference on Harmonisation of Technical Requirements for Registration of Pharmaceuticals for Human Use
ICH E6	ICH Harmonised Tripartite Guideline: Guideline for Good Clinical Practice E6

Abbreviation	Definition
IEC	independent ethics committee
INQoL	Individual quality of life
IP	investigational product
IRB	institutional review board
$K^+$	potassium ion
kg	Kilogram
LEMS	Lambert-Eaton myasthenic syndrome
MedDRA	Medical Dictionary for Regulatory Activities
MG	Myasthenia gravis
mg	Milligram
MI	myocardial infarction
mmHg	millimeters of mercury
MS	multiple sclerosis
NAT	N-acetyl transferase
ng/mL	nanograms per milliliter
NMJ	neuromuscular junction
$PEDSQL^{TM}$	pediatric quality of life inventory
Pgp	P-glycoprotein
PI	Principal Investigator
PK	Pharmacokinetic
PPAS	per protocol analysis set
QMG	Quantitative myasthenia gravis examination
QT	QT wave
QTc	QT wave corrected for heart rate
REB	research ethics board
SAE(s)	serious adverse event(s)
SAF	safety analysis set
SAP	statistical analysis plan
SAS	Statistical Analysis System (software)
SBP	systolic blood pressure
SMA	spinal muscular atrophy
SMN	Survival motor neuron
SOPs	standard operating procedures
$t_{1/2}$	elimination half-life
TEAE(s)	treatment emergent adverse event(s)
TK	Toxicokinetic
$T_{\text{max}}$	time to reach maximum plasma concentration

Abbreviation	Definition
US	United States
WHO-DD	World Health Organization – Drug Dictionary

#### 4 Introduction

This Statistical Analysis Plan (SAP) is based on study procedures and analyses from the protocol, Version 1.0, dated 20 November 2017. This SAP takes as well into account the following protocol versions/amendments:

- Version 2.0, dated 12 April 2019
- Version 3.0, dated 27 September 2019

Table shells and mock listings corresponding to the contents of this document will be prepared and included with the final version. This document, with table shells and mock listings, will be reviewed prior to final unblinded analyses, and revised if necessary.

# 4.1 Background

Spinal Muscular Atrophy (SMA), first described in the 1890s, is an autosomal recessive neuromuscular disease characterized by degeneration of alpha motor neurons in the anterior horn of spinal cord, leading to progressive denervation atrophy in the involved skeletal muscles, with weakness and paralysis. The disease is due to defects in the Survival Motor Neuron 1 (SMN1) gene in chromosome 5, with deficiency in the SMN protein, a ubiquitously expressed protein, critical to the health and survival of the motor neurons.

Recent studies suggest that, due to the ubiquity of SMN protein, SMA might be a multisystem disorder (Hamilton, 2013). The overall incidence of SMA is about 1:6,000-10,000 live births and approximately one in 50 persons are healthy carriers of a defective SMN1 gene (Ogino, 2002, Lunn and Wang 2008). The disease usually appears early in life and is the leading genetic cause of death in infants and toddlers. In most cases, weakness in the legs appears earlier and is generally greater than weakness in the arms. Muscles controlling feeding, swallowing, and respiratory function (e.g., breathing, coughing, and clearing secretions) may also be affected. The clinical phenotype is classified into four types (1, 2, 3, 4), on the basis of age of onset and maximum motor function achieved (Munsat and Davies, 1992 International SMA consortium meeting, (26-28 June 1992, Bonn, Germany). Even within the same type, clinical severity is highly variable and essentially depends on the number of copies of an alternative gene (SMN2), which may produce a limited amount of functional SMN protein, allowing the survival of a variable number of motor neurons. Type 1 patients usually have two copies of the SMN2 gene, or even one copy only, while most Types 3 and 4 patients have three or four copies (Goulet 2013, Kolb 2015). SMA Type 1 (Werdnig-Hoffman disease), the most severe form, appears in the first months of life, often with a very rapid course ("floppy baby syndrome"), and is usually lethal before two years of age. SMA Type 2 also presents very early, before 18 months of age, but symptoms are less severe, and these children are able to sit or even to stand unsupported, although they do not achieve the ability to walk independently. SMA Types 3 and 4 are the least severe forms. In Type 3, symptoms appear after 18 months of age, and severity is highly variable. Many patients have only proximal muscle weakness and can stand and walk independently, sometimes until the late disease stages. Life expectancy is near normal. SMA Type 4 has an adult onset, sometimes after 30 years of age, and muscle weakness, mainly of proximal muscles, is relatively mild and slowly progressing, although loss of independent walking has been rarely reported (Shababi 2014). SMN protein localized in the presynaptic terminals at the neuromuscular junction (NMJ) (Dombert 2014) and its role in NMJ development has been tested by the failure of the cultured muscle cells derived from SMA patients to cluster acetylcholine receptors (AChRs) at the junction (Arnold 2004). In addition, neurofilament accumulation along with poor terminal arborization in postnatal diaphragm samples of SMA Type 1 have been reported (Kariya

2008). Further evidence for a possible role of abnormal NMJ in human SMA pathology derives from a recent study providing a detailed structural characterization of NMJ defects in SMA fetuses (Martinez-Hernandez 2013); main prenatal defects were abnormal modification of acetylcholine receptor clustering, irregular accumulation and positioning of synaptic vesicles, and atypical nerve terminals in motor endplates of SMA Type 1 samples, whereas SMA Type 2 fetuses were similar to controls. In SMA mice some findings suggest skeletal muscle fiber disruption, such as increased activity of cell death pathways (Mutsaers 2011), abnormal differentiation in muscle satellite cells, deficient formation of myotubes, and decreased muscle fiber size (Lee 2011; Hayhurst 2012). Interestingly, loss of murine SMN specifically in the skeletal muscle causes muscle necrosis, paralysis, and death (Cifuentes-Diaz 2001). In addition, restoration of SMN in the mature muscle or increasing the muscle mass through different molecules have limited therapeutic benefits in SMA mice (Gavrilina 2008; Rose 2009; Bosch-Marce 2011), further confirming that NMJ maturation defects and abnormal synapses are the hallmark of SMA pathology (Kariya 2008). There are also data suggesting fatigue and signs of NMJ dysfunction in SMA patients (Montes 2010; Wadman. 2012; Montes 2014; Pera 2017).

Three-Hz repetitive nerve stimulation showed a decremental compound muscle action potential in around half of SMA Types 2 and 3 patients, indicating an impaired NMJ transmission (Wadman 2012; Pera 2017). Furthermore, fatigue tested through 6MWT and expressed as decreased gait speed between first and last minute, is common in SMA Type 3 patients (Montes 2010; Pera 2017). This 6MWT pattern has not been found in other neuromuscular disorders, hence cannot be attributed to muscle weakness alone. Based on the results of a randomized, double-blind, placebo-controlled, phase 3 clinical trial in SMA Types 1, nusinersen, is an antisense, intrathecally administered product designed to bind to the SMN2 pre-mRNA and promote inclusion of exon 7 (Finkel, 2017). It has been recently approved for treatment of all SMA types by FDA and European Medicines Agency. Furthermore, gene-replacement therapy using intravenous administration of adeno-associated virus 9 carrying SMN complementary DNA showed promising results in a small cohort of SMA Type 1 patients (Mendell, 2017). However, it is reasonable to assume that a single therapeutic solution may not be sufficient, hence combined treatments acting on different disease aspects may be beneficial. In summary, recent studies in SMA animal models and SMA patients have shown that the NMJ displays significant structural and functional defects that precede overt disease symptoms, suggesting that impaired NMJ function may contribute to SMA pathogenesis and symptoms. Defects in the NMJ appear to precede degeneration of motor neurons suggesting that abnormal formation and/or maintenance of this structure may be a key event in disease pathogenesis. These defects have been observed at both the pre- and postsynaptic components of the NMJ, which likely contribute to the failure to maintain the NMJ and muscle innervation in mouse models of SMA. Finally, NMJ dysfunction has been also demonstrated in SMA patients, mainly in Type 3 subgroup, contributing to the symptoms associated with the disease.

# 5 Trial Design

## 5.1 Study Objectives

The primary objectives of the study are:

• To characterize the overall safety and tolerability of amifampridine compared with placebo in patients with SMA Type 3; and

 To assess the clinical efficacy of amifampridine compared with placebo in ambulatory patients with SMA Type 3 based on change from baseline in the Hammersmith Functional Motor Scale Expanded (HFMSE) scores.

The secondary objective of the study is to assess the clinical efficacy of amifampridine compared with placebo by using the change from baseline in six-minute walk test, timed tests, and quality of life assessments:

## 5.2 Study Design

This is a stratified, randomized (1:1), double-blind, placebo-controlled, 2-treatment, 2-sequence, crossover study.

Patients will be randomized (1:1) to one of two sequences:

AP: Amifampridine (Period 1) followed by Placebo (Period 2)

PA: Placebo (Period 1) followed by Amifampridine (Period 2)

Patients will be randomized on the last day of the open-label run-in period (Day 0).

IP will be administered under double-blind conditions. Randomized patients who discontinue after initiation of treatment may be replaced. The planned duration of participation for each patient is approximately 2 months, based upon length of dose titration and excluding the screening period, which can last up to 14 days.

The study is planned to be conducted in two investigational sites; and will include about 12 male and female SMA Type 3 patients.

#### 5.3 Study Drug Dosage and Administration

The IP is amifampridine, and it will be provided in round, white-scored tablets, containing amifampridine phosphate formulated to be the equivalent of 10 mg amifampridine base per tablet. Dosing is up to 80 mg/day in 3 or 4 divided doses.

A placebo equivalent will be provided as tablets indistinguishable from the amifampridine tablets and will be administered consistent with the dose regimen of amifampridine.

# 6 Sample Size, Randomization and Blinding

#### 6.1 Sample Size

The sample size for this study was based on clinical considerations related to the epidemiology of the disease, and not on a formal statistical power calculation. It is anticipated approximately 12 patients will be randomized with 6 patients per treatment sequence.

#### 6.2 Randomization and Blinding

Patients will be randomized to one of two sequences:

AP: Amifampridine (Period 1) followed by Placebo (Period 2)

PA: Placebo (Period 1) followed by Amifampridine (Period 2)

This is a double-blind study where all involved parties will be blinded to randomized assignment to the two sequences.

#### **7** Selection and Discontinuation of Patients

## 7.1 Inclusion Criteria

Individuals eligible to participate in this study must meet all the following inclusion criteria:

- 1. Willing and able to provide written informed consent after the nature of the study has been explained and before the start of any research-related procedures.
- 2. Male or female between the ages of 6 and 50 years.
- 3. Genetically confirmed diagnosis of SMA Type 3.
- 4. Able to walk independently for at least 30 meters (objectively measured at screening).
- 5. Not taking Nusinersen for the treatment of SMA (Nusinersen should be stopped at least 6 months before the screening). Salbutamol is permitted only if the dose has been stable for 6 months before screening.
- 6. Able to swallow oral medication.
- 7. Female patients of childbearing potential must have a negative pregnancy test (serum human chorionic gonadotropin [HCG] at screening); and must practice an effective, reliable contraceptive regimen during the study and for up to 30 days following discontinuation of treatment.
- 8. Ability to participate in the study based on overall health of the patient and disease prognosis, as applicable, in the opinion of the Investigator; and able to comply with all requirements of the protocol, including completion of study questionnaires.

#### 7.2 Exclusion Criteria

Individuals who meet any of the following exclusion criteria are not eligible to participate in the study:

- 1. Epilepsy and currently on medication.
- 2. An electrocardiogram (ECG) within 6 months before starting treatment that shows clinically significant abnormalities, in the opinion of the Investigator.
- 3. Breastfeeding or pregnant at Screening or planning to become pregnant at any time during the study.
- 4. Surgery for scoliosis or joint contractures within the previous 6 months.
- 5. Treatment with an investigational drug (other than amifampridine) or device within 6 months before Screening or while participating in this study.
- 6. Any medical condition that, in the opinion of the Investigator, might interfere with the patient's participation in the study, poses an added risk for the patient, or confound the assessment of the patient.
- 7. History of drug allergy to any pyridine-containing substances or any amifampridine excipient(s).
- 8. Less than 3-point improvement in HFMSE from start to end of Run-in period.
- 9. Uncontrolled asthma.
- 10. Concomitant use with sultopride.
- 11. Concomitant use with medicinal products with a narrow therapeutic window.

#### 7.3 Removal of Patients from Treatment or Assessment

Patients may withdraw their consent to participate in the study or to receive treatment at any time without prejudice. The investigator or Catalyst may withdraw a patient from the treatment or from the study at any time.

#### 8 Schedule of Events

The schedule of clinical procedures and assessments conducted during the study is presented in Appendix 1.

# 9 Study Endpoints

### 9.1 Efficacy Endpoints

The following efficacy assessments will be performed as described in the Schedule of Events (Appendix 1), following the sequence in the following listed below.

Order of Assessment at Each Study Visit (when applicable)	Start Time After Dose (+10 minutes unless otherwise specified)	
HFMSE	45 minutes	
6-minute walk test	After HFSME	
Time to rise from floor	After 6-minute walk	
Time to rise from chair	After rise from floor	
Time to climb 4 stairs	After rise from chair	
Time to walk 10 meters	After climb stairs	
Quality of Life Assessment	After 10-meters walk	

# 9.1.1 Hammersmith Functional Motor Scale Expanded (HFMSE)

The HFMSE assess motor function (e.g. lying, rolling, sitting, crawling, attaining standing, walking, running, and jumping) in order of progressive difficulty, with higher values showing higher function abilities. The HFMSE was expanded from the original 20-item Hammersmith functional motor scale by incorporating 13 relevant items to eliminate the "ceiling" effect of the original scale when applied to ambulant SMA patients. Each item scores 2 for unaided, 1 for assistance, and 0 for inability. A total score is calculated by summing the scores of the individual items. The total score can range from 0 (all activities failed) to 66 (all activities achieved unaided). The HFMSE shows good test-retest reliability and correlation with other clinical measures in SMA, especially in Type 3.

#### 9.1.2 6-minute walk test

This is a test of endurance which has been validated for ambulant patients with SMA. Participants are instructed to walk as fast as possible along a 25-meter linear marked course for 6 minutes. Meters walked are recorded.

#### 9.1.3 Timed items

a) Rising from floor – the time required in rising from the supine position

- b) Rising from a chair the time required to stand from a seated position
- c) Climbing 4 steps the time required to climb 4 standardized steps
- d) Walking 10 meters the time required to walk 10 meters as fast as possible

#### 9.1.4 Quality of life assessment

The Individualized Quality of Life for neuromuscular disease (INQoL) or the Pediatric Quality of Life (PEDSQL) will be assessed for adult or pediatric patients, respectively.

# 9.2 Safety Endpoints

Safety endpoints include treatment-emergent adverse events (AEs), vital signs, physical examination, clinical laboratory tests (hematology, chemistry and urinalysis), and ECGs, and each corresponding CFB as appropriate.

## 10 Data Analysis and Statistical Considerations

Statistical tables and by-patient data listings will be prepared using SAS System (SAS Institute, Cary, North Carolina, USA), Version 9.4 under Windows 10 PRO.

## 10.1 Analysis Populations

The following analysis populations have been defined for this clinical study:

- a) Enrolled Population (EP): all patients who provided informed consent for this study.
- b) **Safety Population (SAF)**: the safety population consists of all subjects who are enrolled in the study and have received at least one dose of amifampridine and includes subjects who begin the Run-in period regardless of whether they are randomized to double blind medication on Day 0.
- c) Full Analysis Set (FAS): this population consists of all randomized subjects who receive at least one dose of IP (amifampridine or placebo) and have at least one post-treatment efficacy assessment. Subjects will be compared for efficacy according to the treatment to which they were randomized, regardless of the treatment actually received.
- d) **Per-Protocol Population (PPAS)**: this population is a subset of the FAS population, excluding subjects with major protocol deviations. The PPAS population will include all FAS subjects who:
  - Have no major protocol deviations or inclusion/exclusion criteria deviations that might potentially affect efficacy, and
  - Subjects who took at least 80% of the required treatment doses.

The PPAS population will be determined before database lock and unblinding subject treatment codes.

The FAS population will be the primary analysis set for all effectiveness analyses. The safety population will be used for the analysis of all safety variables and baseline characteristics. The PPAS population will be used for selected effectiveness analyses. The results obtained in PPAS population set will be seen as supportive of those obtained in the FAS population.

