#### 10.12 Safety Data

Summaries of safety data will be presented for the SAF analysis set using observed data only, i.e. without imputation. All observed safety data will be listed.

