**Table 1 - Categories of Severity for Adverse Events** 

Severity	Description	
Grade 1	Mild; asymptomatic or mild symptoms; clinical or diagnostic observations only; intervention not indicated.	
Grade 2	Moderate; minimal, local or noninvasive intervention indicated; limiting age-appropriate instrumental ADL*.	
Grade 3	Severe or medically significant but not immediately life-threatening; hospitalization or prolongation of hospitalization indicated; disabling; limiting self-care ADL**.	
Grade 4	Life-threatening consequences; urgent intervention indicated.	Note: Grade 4 and 5 adverse events should
Grade 5	Death related to AE.	always be reported as serious adverse events

Activities of Daily Living (ADL)

\* Instrumental ADLs refer to preparing meals, shopping for groceries or clothes, using the telephone, managing money, etc.

\*\*Self-care ADLs refer to bathing, dressing and undressing, feeding self, using the toilet, taking medications, and not bedridden.

A treatment-emergent adverse event (TEAE) is any AE that emerges after randomization having been previously absent, or worsens relative to the previous periods. All AEs will be coded using the Medical Dictionary for Regulatory Activities (MedDRA), Version 23.0. All treatment-emergent adverse events (TEAEs) will be summarized by the treatment at the time of onset. Counts and percentages will be presented by treatment for each observed system organ class (SOC) and preferred term (PT) as defined in MedDRA. A patient having more than one TEAE with the same PT in a given time period will be counted only once in the incidence calculation for that PT for that time period. Similarly, if a patient has more than one TEAE in the same SOC in a given time period, the patient will be counted only once in the total number of patients with a TEAE for that SOC for that time period. TEAEs will summarized only for the treatment at onset unless it worsens at subsequent period(s) or recurs after having resolved at a previous period; in each of these situations, the TEAE will be considered a new TEAE and summarized for both treatments.

Each TEAE will be assessed with respect to severity and relationship to treatment. The relationship of an AE will be recorded using the specified relationship categories described in Table 2.

Table 2 - Description of relationship to adverse events categories

Relationship	
Category	Description
Not Related	Exposure to the IP has not occurred
	OR

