#### 13 Table Shells and Specifications

# 13.1 Table Specifications

Tables will be provided as defined by the table shells.

Similar tables based on different populations will have the same number, except for the last digit.

All output will be generated by SAS and exported into a Microsoft Word document in RTF format. All output will be in landscape orientation. Left and right margins will be 2 cm from the side; the top and bottom margins will be 2.5 cm. Font size will be Courier New 7 pt.

The header containing the sponsor name (Catalyst Pharmaceuticals) and protocol number will appear on the top left corner of each page of the output. The page number, in the format of "Page x of y", will appear on the top right corner of the output, where y = last page of corresponding output.

Column headers in tables include the total possible numbers to be included in summaries for that table, designated as "(N=XX)".

The SAS program name, the date of the creation of the output (run date) and the reference to the data listing(s) from which the table is derived will appear on the bottom left corner as follows:

Source: [program name].sas, Run on ddmmmyyyy

Source: Listing(s) xx.x.x, xx.x.x

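### TEAE percentages are placed on a safety population that includes patients never randomized, who cannot have a TEAE, and the column denominator is not stated

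*SAP*

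**What the plan says.** - **Analysis set.** SAP 10.1 defines the SAF as enrolled patients with at least one amifampridine dose, and adds that it "includes subjects who begin the Run-in period regardless of whether they are randomized to double blind medication on Day 0". Protocol 14.2 has the same definition. Both documents assign this set to all safety variables and baseline characteristics. SAP 10.12 repeats it: "Summaries of safety data will be presented for the SAF analysis set using observed data only, i.e. without imputation".
- **What counts as an event.** SAP 10.12.1: "A treatment-emergent adverse event (TEAE) is any AE that emerges after randomization having been previously absent, or worsens relative to the previous periods". TEAEs "will be summarized by the treatment at the time of onset". Events that start on open-label drug before Day 0 go to a listing (the tenth listing in 10.12.1). None of the nine planned AE summary tables covers run-in.
- **Denominator.** SAP 10.12.1 asks for TEAE counts and percentages by treatment, system organ class and preferred term, but does not say what the percentages are taken over. The only general rule is in SAP 13.1: "Column headers in tables include the total possible numbers to be included in summaries for that table".
- **Why run-in failures are expected.** Exclusion criterion 8 (Protocol 9.2.2, SAP 7.2) bars from randomization anyone who gains fewer than 3 HFMSE points during run-in.
- **Patients never randomized.** SAP 14 gives them a category of their own, but only for listings.

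**The concern.** The numerator and the named analysis set describe different groups. The numerator is restricted to time after randomization, while the set reaches back to the first open-label dose. Patients who fail the HFMSE gate have no time after randomization, so each one adds to N and can add nothing to the count.

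This matters because safety and tolerability compared with placebo is the first primary objective (Protocol 8.1.1, SAP 5.1), and the protocol synopsis limits the AE analysis to TEAEs. The by-treatment TEAE percentages are therefore the main AE comparison. With about 12 randomized patients, a few extra in N change them visibly.

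The same gap affects the layout of other tables. Demographics, vital signs, ECG, physical examination and laboratory tables are planned on the SAF but shown by sequence (SAP 10.2, 10.9.1, 10.12.2 to 10.12.5). Run-in failures have no sequence, so they would be dropped or placed by a rule that is not written. This is mainly a presentation problem and does not itself bias one treatment against the other.

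**Working it through.** **Plan's own figure.** There is no TEAE rate, TEAE denominator, run-in pass rate or number entering run-in to reproduce. The one relevant figure is the number randomized: 2 sequences × 6 patients = 12 (SAP 6.1), which the plan states is not based on a power calculation.

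**Inputs**
- R = 12 randomized, all assumed to take both treatments (SAP 6.1, crossover design).
- F = patients dosed in run-in but never randomized. This is not in the documents, so a range is shown.
- For illustration only, TEAEs in 6 patients on amifampridine and 3 on placebo. These counts are assumed.

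**Step 1: effect of a literal SAF denominator.** The SAF has R + F patients and run-in failures add no events, so a reported percentage equals the double-blind percentage times R/(R+F):
- F=3: 12/15 = 0.80
- F=4: 12/16 = 0.75
- F=6: 12/18 = 0.67
- F=12: 12/24 = 0.50
- F=24: 12/36 = 0.33

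**Step 2: three denominators that the text allows**
- (a) Patients given that treatment in the double-blind periods: N = 12 in each column.
- (b) SAF patients who received that treatment. Every SAF patient received amifampridine by definition, so N = 12+F for amifampridine and 12 for placebo.
- (c) The whole SAF in both columns: N = 12+F in each.

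| Reading | F | Amifampridine | Placebo | Ratio | Difference (points) |
|---|---|---|---|---|---|
| (a) | any | 6/12 = 50.0% | 3/12 = 25.0% | 2.00 | 25.0 |
| (b) | 3 | 6/15 = 40.0% | 3/12 = 25.0% | 1.60 | 15.0 |
| (b) | 6 | 6/18 = 33.3% | 3/12 = 25.0% | 1.33 | 8.3 |
| (b) | 12 | 6/24 = 25.0% | 3/12 = 25.0% | 1.00 | 0.0 |
| (c) | 3 | 6/15 = 40.0% | 3/15 = 20.0% | 2.00 | 20.0 |
| (c) | 6 | 6/18 = 33.3% | 3/18 = 16.7% | 2.00 | 16.7 |
| (c) | 12 | 6/24 = 25.0% | 3/24 = 12.5% | 2.00 | 12.5 |

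**Step 3: reading the table.** Under (a) F has no effect. Under (c) both rates and the difference shrink by the same factor and the ratio stays at 2.00; the placebo column also counts patients who never took placebo. Under (b) only amifampridine shrinks. If the true rates were equal at 6/12 each, (b) with F=4 would show 6/16 = 37.5% against 50%.

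**The case against.** The best reply is that the SAP can be read as (a).
- TEAEs are assigned to the treatment at onset.
- SAP 10.10.2 summarizes double-blind duration and compliance on the same SAF, by treatment and period, with formulas that start at Day 0 or Day 14. Run-in failures cannot contribute there, so the SAP already uses the SAF by treatment to mean those with data on that treatment.
- The header rule in SAP 13.1 could be taken to exclude anyone who cannot appear in a post-randomization table.
- SAP 4 and 13.1 leave table layout to the shells, which may set N correctly.

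In addition, safety is descriptive (protocol synopsis), only the primary efficacy comparison is confirmatory (SAP 10.3), and counts are shown beside percentages, so a reader could recompute the rates.

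Much of this stands. It shows that (a) is possible and lowers the severity, but it does not make (a) the written rule. SAP 10.12 names the SAF, none of the four populations in SAP 10.1 is a double-blind safety set, and the header rule fits (c) as easily as (a).

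A reader might go further and infer that the plan, as written, dilutes amifampridine's AE rate by up to half and makes the drug look safer than placebo. The documents do not support that. One-sided dilution occurs only under (b), which is plausible but not written. Halving needs 12 run-in failures for 12 randomized, a number with no source in the documents, and it is not a limit: F=24 gives 0.33. It would also be too strong to say that a TEAE must start after randomization, because a run-in event that later worsens counts. That exception does not help run-in failures, who have no later period.

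**Conclusion.** The mismatch is real and follows directly from the text: patients who fail run-in belong to the set named for TEAE summaries and cannot have a TEAE. Applied literally, the SAF understates TEAE percentages by 12/(12+F), which is 0.80, 0.67 and 0.50 at F = 3, 6 and 12. Whether the comparison with placebo is also biased depends on an unstated denominator: the ratio is preserved if both columns use the SAF, and shifts in favour of amifampridine if N is SAF patients who received that treatment.

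This rests on 12 randomized patients who all take both treatments, on an F that the documents do not give, and on table shells that could not be checked. Because the safety analysis is descriptive and counts are shown, this should be fixed before unblinding but does not threaten the trial's primary efficacy inference. Severity: SHOULD-FIX.

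**What to change.** - In SAP 10.1, add a double-blind safety set: randomized patients who took at least one blinded dose.
- In SAP 10.12.1, state that N in each TEAE column is the number of patients with at least one blinded dose of that column's treatment, and carry this into the shells. The dilution factor is then 1.00 whatever F is.
- Keep the SAF for run-in outputs. Add a run-in AE summary table with all patients dosed in run-in as denominator. This also brings into a table those events that start on open-label drug and persist without worsening, which the TEAE tables leave out under any denominator.
- In SAF tables shown by sequence, add a column for patients not randomized, to match the category that SAP 14 already uses in listings.

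The cost is SAP wording, table headers and a little more table work. No data collection changes. Reported TEAE percentages may be higher than under a literal SAF denominator.
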